6. PROTOCOL DEVIATIONS

All protocol deviations will be reviewed by the project team prior to database lock to identify subjects with major protocol deviations.

Reported deviations from the protocol will be listed by subject and date. The type of deviation along with a description and any additional comments about the deviation will be listed.

7. CHANGES IN THE PLANNED ANALYSES

Based on FDA Guidance an analysis of Cohort 1 + Cohort 2 is now planned as the primary efficacy population. In particular, the FDA has stated that recurrence of bladder cancer within 12 months of BCG is an acceptable study population for investigational agents in this setting.

No other changes to the protocol planned analyses have been described. Should changes arise, these changes will be fully described in the Clinical Study Report.

Following the completion of the protocol-specified analyses, the sponsor may choose to conduct additional exploratory analyses. Such analyses will be detailed in a separate document.

8. **REVISION HISTORY**

Date	Revision	Rationale
27OCT2020	Updated Section 3.3.8 by study visit windows for maintenance month and long-term follow-up windows	Updated for 3 months to cover 91 days (i.e. 13 weeks) instead of 12 weeks for consistency with response assessments which occur every 13 weeks during maintenance.
27OCT2020	Removed third sensitivity analysis for efficacy endpoints	Data collection did not allow for determination of upper and lower tract disease.

9. **PROGRAMMING CONVENTIONS**

- Page orientation, margins, and fonts: Summary tables, listings, and figures will appear in landscape orientation. There should be a minimum of a 1.25" boundary on the upper (bound) edge, and a minimum of a 1.0" boundary on the remaining three edges. Output should be printed in Courier New with a point size of 8. Titles may be printed using a larger font (e.g., Arial point size 10).
- Identification of analysis population: Every summary table and figure should clearly specify the analysis population being summarized. Listings will be prepared for all enrolled subjects.
- Group headers: In the summary tables, the group headers will identify the cohort and the within-group sample size for the indicated analysis population. Of note, the header's sample size does not necessarily equal the number of subjects actually summarized within any given summary module; some subjects in the analysis population may have missing values and thus may not be summarized.
- Suppression of percentages corresponding to null categories: When count data are presented as category frequencies and corresponding percentages, the percent should be suppressed when the count is zero in order to draw attention to the non-zero counts.
- Presentation of sample sizes: Summary modules should indicate, in one way or another, the number of subjects actually contributing to the summary statistics presented in any given summary module. As mentioned above, this may be less than the number of subjects in the analysis population.
 - ◆ In the quantitative modules describing continuous variables (and thus presenting sample size, means, and standard deviations), the sample size should be the number of non-missing observations
 - ◆ For categorical variables that are presented in frequency tables, the module should present the total count in addition to the count in each category. Percentages should be calculated using this total as the denominator, and the percentage corresponding to the sum itself (that is, 100%) should be presented to indicate clearly to a reviewer the method of calculation.
- Sorting: Listings will be sorted first by subject number and then by phase (induction, maintenance), visit, and date, if applicable. If a listing is sorted in a different manner, a footnote will indicate as such.
- General formatting rules: Rounding for all variables will occur only as the last step, immediately prior to presentation in listings, tables, and figures. No intermediate rounding will be performed on derived variables. The standard rounding practice of rounding numbers ending in 0-4 down and numbers ending in 5-9 up will be employed.
- The presentation of numerical values will adhere to the following guidelines:
 - ◆ Raw measurements will be reported to the number of significant digits as captured electronically or on the CRFs.
 - ◆ Standard deviations will be reported to one decimal place beyond the number of decimal places the original parameter is presented.
 - ◆ Means will be reported to the same number of significant digits as the parameter.
 - ◆ Calculated percentages will be reported with no decimals.

- Dates will be formatted as DDMMYYYY. Partial dates will be presented on data listings as recorded on CRFs.
 - ◆ Time will be presented according to the 24-hour clock (HHMM).

10. PROPOSED TABLES, LISTINGS, AND FIGURES DSMB ANALYSES

Summary Tables

Table 1 Eligibility, Enrollment, and Treatment Status, All Consented Subjects

Table 2 Subject Termination from Study, Safety Population

Table 3 Demographics, Safety Population

Table 4 Baseline Disease Characteristics, Safety Population

Table 5 Treatment-Emergent Adverse Events by System Organ Classification, Preferred Term, and Greatest Severity, Safety Population

Table 6 Treatment-Emergent Adverse Events Related to Vicinium by System Organ Classification, Preferred Term, and Greatest Severity, Safety Population

Table 7 Treatment-Emergent Serious Adverse Events by System Organ Classification, Preferred Term, and Greatest Severity, Safety Population

Table 8 Clinical Laboratory Assessments by Visit, Safety Population

Table 9 Graded Laboratory Toxicities, Safety Population

Table 10 Worst Post-Baseline Laboratory Shifts, Safety Population

Table 11 Vital Signs, Weight, and Height by Visit, Safety Population

Table 12 Electrocardiogram by Visit, Safety Population

Table 13 Summary of Complete Response by Visit, Ongoing Subjects Are Excluded as 'Missing', mITT Population

Data Listings

Listing 1 Study Completion, Safety Population

Listing 2 Demographics, Safety Population

Listing 3 Adverse Events, Safety Population

Listing 3.1 Serious Adverse Events, Safety Population

Listing 4.1.1 Select Chemistry Results for Subjects with a Post-Baseline Abnormality, Safety Population

Listing 4.1.2 Clinical Chemistry Laboratory Data, Safety Population

Listing 4.2.1 Select Hematology Results for Subjects with a Post-Baseline Abnormality, Safety Population

Listing 4.2.2 Hematology Laboratory Data, Safety Population

Listing 4.3.1 Select Urinalysis Results for Subjects with a Post-Baseline Abnormality, Safety Population

Listing 4.3.2 Urinalysis Laboratory Data, Safety Population

Listing 5 Study Drug Administration, Safety Population

Listing 6 Efficacy Assessments, Safety Population

Listing 7 Vital Signs, Height, and Weight, Safety Population

Listing 8 Electrocardiogram, Safety Population

Listing 9 BCG Treatment History, Enrolled Population

Figures

Figure 1 Clinical Laboratory Assessments by Visit, Safety Population: Subjects with a Treatment Emergent Grade 3 or Higher Event

Figure 2.1 Alanine Aminotransferase (IU/L) by Visit vs. Baseline, Safety Population

Figure 2.2 Alkaline Phosphatase (IU/L) by Visit vs. Baseline, Safety Population

Figure 2.3 Aspartate Aminotransferase (IU/L) by Visit vs. Baseline, Safety Population

Figure 2.4 Bilirubin (mg/dL) by Visit vs. Baseline, Safety Population

Figure 2.5 Creatinine (mg/dL) by Visit vs. Baseline, Safety Population

Figure 2.6 Hemoglobin (g/L) by Visit vs. Baseline, Safety Population

Figure 2.7 Leukocytes ($10^9/L$) by Visit vs. Baseline, Safety Population

Figure 2.8 Lymphocytes ($10^9/L$) by Visit vs. Baseline, Safety Population

Figure 2.9 Neutrophils ($10^9/L$) by Visit vs. Baseline, Safety Population

Figure 2.10 Platelets ($10^9/L$) by Visit vs. Baseline, Safety Population

Figure 3.1 Time on Treatment by Disease Cohort, Safety Population

Figure 3.2 Time on Treatment, Safety Population

11. **TABLES, LISTINGS, AND FIGURES 6 MONTH ANALYSIS**

Summary Tables

Table 1 Eligibility, Enrollment, and Treatment Status, All Consented Subjects

Table 2 Subject Termination from Study, Safety Population

Table 3 Demographics, Safety Population

Table 4 Baseline Disease Characteristics, Safety Population

Table 5 Treatment-Emergent Adverse Events by System Organ Classification, Preferred Term, and Greatest Severity, Safety Population

Table 6 Treatment-Emergent Adverse Events Related to Vicinium by System Organ Classification, Preferred Term, and Greatest Severity, Safety Population

Table 7 Treatment-Emergent Serious Adverse Events by System Organ Classification, Preferred Term, and Greatest Severity, Safety Population

Table 8 Clinical Laboratory Assessments by Visit, Safety Population

Table 9 Graded Laboratory Toxicities, Safety Population

Table 10 Worst Post-Baseline Laboratory Shifts, Safety Population

Table 11 Vital Signs, Weight, and Height by Visit, Safety Population

Table 12 Electrocardiogram by Visit, Safety Population

Table 13 Summary of Complete Response by Visit, Ongoing Subjects Are Excluded as 'Missing', mITT Population

Table 14 Cystectomy-Free Days, mITT Population

Data Listings

Listing 1 Study Completion, Safety Population

Listing 2 Demographics, Safety Population

Listing 3 Adverse Events, Safety Population

Listing 3.1 Serious Adverse Events, Safety Population

Listing 4.1.1 Select Chemistry Results for Subjects with a Post-Baseline Abnormality, Safety Population

Listing 4.1.2 Clinical Chemistry Laboratory Data, Safety Population

Listing 4.2.1 Select Hematology Results for Subjects with a Post-Baseline Abnormality, Safety Population

Listing 4.2.2 Hematology Laboratory Data, Safety Population

Listing 4.3.1 Select Urinalysis Results for Subjects with a Post-Baseline Abnormality, Safety Population

Listing 4.3.2 Urinalysis Laboratory Data, Safety Population

Listing 5 Study Drug Administration, Safety Population

Listing 6 Efficacy Assessments, Safety Population

Listing 7 Vital Signs, Height, and Weight, Safety Population

Listing 8 Electrocardiogram, Safety Population

Listing 9 BCG Treatment History, Enrolled Population

Figures

Figure 1 Clinical Laboratory Assessments by Visit, Safety Population: Subjects with a Treatment Emergent Grade 3 or Higher Event

Figure 2.1 Alanine Aminotransferase (IU/L) by Visit vs. Baseline, Safety Population

Figure 2.2 Alkaline Phosphatase (IU/L) by Visit vs. Baseline, Safety Population

Figure 2.3 Aspartate Aminotransferase (IU/L) by Visit vs. Baseline, Safety Population

Figure 2.4 Bilirubin (mg/dL) by Visit vs. Baseline, Safety Population

Figure 2.5 Creatinine (mg/dL) by Visit vs. Baseline, Safety Population

Figure 2.6 Hemoglobin (g/L) by Visit vs. Baseline, Safety Population

Figure 2.7 Leukocytes ($10^9/L$) by Visit vs. Baseline, Safety Population

Figure 2.8 Lymphocytes ($10^9/L$) by Visit vs. Baseline, Safety Population

Figure 2.9 Neutrophils ($10^9/L$) by Visit vs. Baseline, Safety Population

Figure 2.10 Platelets ($10^9/L$) by Visit vs. Baseline, Safety Population

Figure 3.1 Time on Treatment by Disease Cohort, Safety Population

Figure 3.2 Time on Treatment, Safety Population

12. **PROPOSED TABLES, LISTINGS, AND FIGURES FINAL ANALYSIS**

Summary Tables

Accountability and Baseline Characteristics

- 14.1.1 Eligibility, Enrollment and Treatment Status
- 14.1.2 Subject Termination from Study
- 14.1.3 Demographics
- 14.1.4 Baseline Disease Characteristics

Efficacy

- 14.2.1.1.1 Summary of Complete Response by Visit – Primary Efficacy Population
- 14.2.1.1.2 Summary of Complete Response by Initial Disease Group and Visit – Primary Efficacy Population
- 14.2.1.1.3 Summary of Complete Response by Subgroup and Visit – Primary Efficacy Population
- 14.2.1.2.1 Summary of Complete Response by Visit, Sensitivity Assessments – Primary Efficacy Population
- 14.2.1.2.2 Summary of Complete Response by Visit, Sensitivity Assessments – Low Grade Ta as Failure - Primary Efficacy Population
- 14.2.1.4 Summary of Complete Response by Visit – Evaluable Population
- 14.2.1.5 Summary of Complete Response by Visit – Induction Phase Dosing Compliant Population
- 14.2.1.6 Summary of Complete Response by Visit – Study Dosing Compliant Population
- 14.2.1.7.1 Summary of Recurrence-free Subjects by Visit – mITT Population - Cohort 3
- 14.2.1.7.2 Summary of Recurrence-free Subjects by Initial Disease Group and Visit – mITT – Cohort 3
- 14.2.1.8 Summary of Recurrence-free Subjects by Visit – Evaluable Population
- 14.2.1.9 Summary of Recurrence-free Subjects by Visit – Induction Phase Dosing Compliant Population
- 14.2.1.10 Summary of Recurrence-free Subjects by Visit – Study Dosing Compliant Population
- 14.2.2.1.1 Duration of Response – Primary Efficacy Population
- 14.2.2.1.2 Duration of Response by Age Subgroup – Primary Efficacy Population
- 14.2.2.1.3 Duration of Response by Gender Subgroup – Primary Efficacy Population
- 14.2.2.1.4 Duration of Response by Region Subgroup – Primary Efficacy Population
- 14.2.2.1.5 Duration of Response by Race Subgroup – Primary Efficacy Population
- 14.2.2.1.6 Duration of Response by Prior BCG Therapies Subgroup – Primary Efficacy Population
- 14.2.2.1.7 Duration of Response by Instillation Subgroup – Primary Efficacy Population
- 14.2.2.2.1 Duration of Response, Sensitivity Assessments – Primary Efficacy Population
- 14.2.2.2.2 Duration of Response, Sensitivity Assessments - Low Grade Ta as Failure – Primary Efficacy Population
- 14.2.2.6 Duration of Response – Evaluable Population
- 14.2.2.7 Duration of Response – Induction Phase Dosing Compliant Population
- 14.2.2.8 Duration of Response – Study Dosing Compliant Population
- 14.2.3.1.1 Event-free Survival – mITT Population
- 14.2.3.1.2 Event-free Survival by Age Subgroup – mITT Population
- 14.2.3.1.3 Event-free Survival by Gender Subgroup – mITT Population
- 14.2.3.1.4 Event-free Survival by Region Subgroup – mITT Population
- 14.2.3.1.5 Event-free Survival by Race Subgroup – mITT Population
- 14.2.3.1.6 Event-free Survival by Prior BCG Therapies Subgroup – mITT Population
- 14.2.3.1.7 Event-free Survival by Instillation Subgroup – mITT Population

- 14.2.3.3 Event-free Survival – Evaluable Population
- 14.2.3.4 Event-free Survival – Induction Phase Dosing Compliant Population
- 14.2.3.5 Event-free Survival – Study Dosing Compliant Population
- 14.2.4.1.1 Cystectomy-Free Days – mITT Population
- 14.2.4.1.2 Cystectomy-Free Days by Age Subgroup – mITT Population
- 14.2.4.1.3 Cystectomy-Free Days by Gender Subgroup – mITT Population
- 14.2.4.1.4 Cystectomy-Free Days by Region Subgroup – mITT Population
- 14.2.4.1.5 Cystectomy-Free Days by Race Subgroup – mITT Population
- 14.2.4.1.6 Cystectomy-Free Days by Prior BCG Therapies Subgroup – mITT Population
- 14.2.4.1.7 Cystectomy-Free Days by Instillation Subgroup – mITT Population
- 14.2.4.3 Cystectomy-Free Days – Evaluable Population
- 14.2.4.4 Cystectomy-Free Days – Induction Phase Dosing Compliant Population
- 14.2.4.5 Cystectomy-Free Days – Study Dosing Compliant Population
- 14.2.4.6 Cystectomy-Free Days, Responders vs Non-responders – Primary Efficacy Population
- 14.2.5.1.1 Time to Disease Recurrence – mITT Population – Cohort 3
- 14.2.5.1.2 Time to Disease Recurrence by Age Subgroup – mITT Population – Cohort 3
- 14.2.5.1.3 Time to Disease Recurrence by Gender Subgroup – mITT Population – Cohort 3
- 14.2.5.1.4 Time to Disease Recurrence by Region Subgroup – mITT Population – Cohort 3
- 14.2.5.1.5 Time to Disease Recurrence by Race Subgroup – mITT Population – Cohort 3
- 14.2.5.1.6 Time to Disease Recurrence by Prior BCG Therapies Subgroup – mITT Population – Cohort 3
- 14.2.5.1.7 Time to Disease Recurrence by Instillation Subgroup – mITT Population – Cohort 3
- 14.2.5.3 Time to Disease Recurrence – Evaluable Population – Cohort 3
- 14.2.5.4 Time to Disease Recurrence – Induction Phase Dosing Compliant Population – Cohort 3
- 14.2.5.5 Time to Disease Recurrence – Study Dosing Compliant Population – Cohort 3
- 14.2.6.1.1 Progression-free Survival – mITT Population
- 14.2.6.1.2 Progression-free Survival by Age Subgroup – mITT Population
- 14.2.6.1.3 Progression-free Survival by Gender Subgroup – mITT Population
- 14.2.6.1.4 Progression-free Survival by Region Subgroup – mITT Population
- 14.2.6.1.5 Progression-free Survival by Race Subgroup – mITT Population
- 14.2.6.1.6 Progression-free Survival by Prior BCG Therapies Subgroup – mITT Population
- 14.2.6.1.7 Progression-free Survival by Instillation Subgroup – mITT Population
- 14.2.6.3 Progression-free Survival – Evaluable Population
- 14.2.6.4 Progression-free Survival – Induction Phase Dosing Compliant Population
- 14.2.6.5 Progression-free Survival – Study Dosing Compliant Population
- 14.2.7.1.1 Overall Survival – mITT Population
- 14.2.7.1.2 Overall Survival by Age Subgroup – mITT Population
- 14.2.7.1.3 Overall Survival by Gender Subgroup – mITT Population
- 14.2.7.1.4 Overall Survival by Region Subgroup – mITT Population
- 14.2.7.1.5 Overall Survival by Race Subgroup – mITT Population
- 14.2.7.1.6 Overall Survival by Prior BCG Therapies Subgroup – mITT Population
- 14.2.7.1.7 Overall Survival by Instillation Subgroup – mITT Population
- 14.2.7.3 Overall Survival – Evaluable Population
- 14.2.7.4 Overall Survival – Induction Phase Dosing Compliant Population
- 14.2.7.5 Overall Survival – Study Dosing Compliant Population

Safety

- 14.3.1.1.1 Treatment-Emergent Adverse Events by System Organ Classification, Preferred Term, and Greatest Severity
- 14.3.1.1.2 Treatment-Emergent Adverse Events By System Organ Classification, Preferred Term, and Greatest Severity – Age Subgroup
- 14.3.1.1.3 Treatment-Emergent Adverse Events By System Organ Classification, Preferred Term, and Greatest Severity – Gender Subgroup
- 14.3.1.1.4 Treatment-Emergent Adverse Events By System Organ Classification, Preferred Term, and Greatest Severity – Region Subgroup
- 14.3.1.1.5 Treatment-Emergent Adverse Events By System Organ Classification, Preferred Term, and Greatest Severity – Race Subgroup
- 14.3.1.1.6 Treatment-Emergent Adverse Events By System Organ Classification, Preferred Term, and Greatest Severity – Prior BCG Therapies Subgroup
- 14.3.1.1.7 Treatment-Emergent Adverse Events By System Organ Classification, Preferred Term, and Greatest Severity – Instillation Subgroup
- 14.3.1.2.1 Treatment-Emergent Adverse Events Related to Vicinium By System Organ Classification, Preferred Term, and Greatest Severity
- 14.3.1.2.2 Treatment-Emergent Adverse Events Related to Vicinium By System Organ Classification, Preferred Term, and Greatest Severity – Age Subgroup
- 14.3.1.2.3 Treatment-Emergent Adverse Events Related to Vicinium By System Organ Classification, Preferred Term, and Greatest Severity – Gender Subgroup
- 14.3.1.2.4 Treatment-Emergent Adverse Events Related to Vicinium By System Organ Classification, Preferred Term, and Greatest Severity – Region Subgroup
- 14.3.1.2.5 Treatment-Emergent Adverse Events Related to Vicinium By System Organ Classification, Preferred Term, and Greatest Severity – Race Subgroup
- 14.3.1.2.6 Treatment-Emergent Adverse Events Related to Vicinium By System Organ Classification, Preferred Term, and Greatest Severity – Prior BCG Therapies Subgroup
- 14.3.1.2.7 Treatment-Emergent Adverse Events Related to Vicinium By System Organ Classification, Preferred Term, and Greatest Severity – Instillation Subgroup
- 14.3.1.3 Treatment-Emergent Adverse Events Leading to the Discontinuation of Study Drug by System Organ Classification, Preferred Term, and Greatest Severity
- 14.3.1.4.1 Treatment-Emergent Serious Adverse Events by System Organ Classification, Preferred Term, and Greatest Severity
- 14.3.1.4.2 Treatment-Emergent Serious Adverse Events by System Organ Classification, Preferred Term, and Greatest Severity – Age Subgroup
- 14.3.1.4.3 Treatment-Emergent Serious Adverse Events by System Organ Classification, Preferred Term, and Greatest Severity – Gender Subgroup
- 14.3.1.4.4 Treatment-Emergent Serious Adverse Events by System Organ Classification, Preferred Term, and Greatest Severity – Region Subgroup
- 14.3.1.4.5 Treatment-Emergent Serious Adverse Events by System Organ Classification, Preferred Term, and Greatest Severity – Race Subgroup
- 14.3.1.4.6 Treatment-Emergent Serious Adverse Events by System Organ Classification, Preferred Term, and Greatest Severity – Prior BCG Therapies Subgroup
- 14.3.1.4.7 Treatment-Emergent Serious Adverse Events by System Organ Classification, Preferred Term, and Greatest Severity – Instillation Subgroup
- 14.3.1.5.1 Treatment-Emergent Adverse Events by System Organ Classification, Preferred Term, and Severity Group
- 14.3.1.5.2 Treatment-Emergent Adverse Events Occurring in at Least 5% of Subjects by System Organ Classification, Preferred Term, and Severity Group

- 14.3.1.5.3 Treatment-Emergent Adverse Events Occurring in at Least 3% of Subjects by System Organ Classification, Preferred Term, and Severity Group
- 14.3.1.5.4 Treatment-Emergent Adverse Events Occurring in at Least 2% of Subjects by System Organ Classification, Preferred Term, and Severity Group
- 14.3.1.6.1 Treatment-Emergent Adverse Events Related to Vicinium by System Organ Classification, Preferred Term, and Severity Group
- 14.3.1.6.2 Treatment-Emergent Adverse Events Related to Vicinium Occurring in at Least 5% of Subjects by System Organ Classification, Preferred Term, and Severity Group
- 14.3.1.6.3 Treatment-Emergent Adverse Events Related to Vicinium Occurring in at Least 3% of Subjects by System Organ Classification, Preferred Term, and Severity Group
- 14.3.1.6.4 Treatment-Emergent Adverse Events Related to Vicinium Occurring in at Least 2% of Subjects by System Organ Classification, Preferred Term, and Severity Group
- 14.3.1.7 Treatment-Emergent Serious Adverse Events by System Organ Classification, Preferred Term, and Severity Group
- 14.3.1.8 Treatment-Emergent Adverse Events by Preferred Term
- 14.3.1.9 Treatment-Emergent Adverse Events Related to Vicinium by Preferred Term
- 14.3.1.10 Treatment-Emergent Adverse Events Leading to Discontinuation of Vicinium by Preferred Term
- 14.3.1.11 Treatment-Emergent Serious Adverse Events by Preferred Term
- 14.3.1.12 Treatment-Emergent Serious Adverse Events Related to Vicinium by Preferred Term
- 14.3.1.13.1 Treatment-Emergent Adverse Events by System Organ Classification, Preferred Term, and Greatest Severity – Adverse Events with Severity of Grade 3 or Higher
- 14.3.1.13.2 Treatment-Emergent Adverse Events by System Organ Classification, Preferred Term, and Greatest Severity – Adverse Events with Severity of Grade 3 or Higher – Age Subgroup
- 14.3.1.13.3 Treatment-Emergent Adverse Events by System Organ Classification, Preferred Term, and Greatest Severity – Adverse Events with Severity of Grade 3 or Higher – Gender Subgroup
- 14.3.1.13.4 Treatment-Emergent Adverse Events by System Organ Classification, Preferred Term, and Greatest Severity – Adverse Events with Severity of Grade 3 or Higher – Region Subgroup
- 14.3.1.13.5 Treatment-Emergent Adverse Events by System Organ Classification, Preferred Term, and Greatest Severity – Adverse Events with Severity of Grade 3 or Higher – Race Subgroup
- 14.3.1.13.6 Treatment-Emergent Adverse Events by System Organ Classification, Preferred Term, and Greatest Severity – Adverse Events with Severity of Grade 3 or Higher – Prior BCG Therapies Subgroup
- 14.3.1.13.7 Treatment-Emergent Adverse Events by System Organ Classification, Preferred Term, and Greatest Severity – Adverse Events with Severity of Grade 3 or Higher – Instillation Subgroup
- 14.3.4.1.1 Clinical Laboratory Assessments by Visit
- 14.3.4.2 Treatment-Emergent Laboratory Toxicities
- 14.3.4.3 Worst Post Baseline Laboratory Shifts
- 14.3.5 Vital Signs by Visit
- 14.3.6 ECG by Visit
- 14.3.7 Concomitant Medications by Generic Name and Drug Classification
- 14.3.8 Serum Vicinium Concentrations

Data Listings

- 16.2.1 Study Completion
- 16.2.2.1 Informed Consent, Eligibility, and Inclusion/Exclusion Criteria
- 16.2.2.2 Protocol Deviations
- 16.2.4 Demographics
- 16.2.5.1.1 Study Drug Administration
- 16.2.5.1.2 Plasma Vicinium Sample Collection
- 16.2.5.2.1 Previous and Concomitant Medications
- 16.2.5.2.2 Medical History
- 16.2.5.2.3 Bladder Cancer History
- 16.2.5.2.4 Cancer Treatment History
- 16.2.5.2.5 BCG Treatment History
- 16.2.5.2.6 Non-Drug Therapy Procedures
- 16.2.5.2.7 Anesthesia
- 16.2.6.1.1 Cystoscopy Procedure
- 16.2.6.1.2 Cystoscopy Findings
- 16.2.6.2 Central Pathology Reader
- 16.2.6.3.1 Urine Cytology
- 16.2.6.3.2 Urine Cytology Reader
- 16.2.6.4 Biopsy
- 16.2.6.5.1 Efficacy Endpoint Summary
- 16.2.6.5.2 Response Summary – Primary Efficacy Population
- 16.2.6.5.3 Time to Event Summary – mITT Population
- 16.2.6.5.4 Time to Event Summary – Evaluable Population
- 16.2.6.5.5 Time to Event Summary – Induction Phase Dosing Compliant Population
- 16.2.6.5.6 Time to Event Summary – Study Dosing Compliant Population
- 16.2.7.1 Adverse Events
- 16.2.7.2 Serious Adverse Events
- 16.2.7.3 Adverse Events by Age Group, System Organ Classification, and Preferred Term
- 16.2.7.4 Related Adverse Events by Age Group, System Organ Classification, and Preferred Term
- 16.2.7.5 Serious Adverse Events by Age Group, System Organ Classification, and Preferred Term
- 16.2.8.1.X Laboratory Values
 - ◆ Select Chemistry Results for Subjects with a Post-Baseline Abnormality
 - ◆ Chemistry
 - ◆ Select Hematology Results for Subjects with a Post-Baseline Abnormality
 - ◆ Hematology
 - ◆ Select Urinalysis Results for Subjects with a Post-Baseline Abnormality
 - ◆ Urinalysis (Includes Pregnancy Test)
- 16.2.8.2 Vital Signs, Height and Weight
- 16.2.8.3 Physical Examinations
- 16.2.8.4 12-Lead Electrocardiogram
- 16.2.8.5 Transurethral Resection of Bladder Tumors (TURBT)
- 16.2.8.6 Prostatic Urethral Biopsy
- 16.2.8.7 Radiological Imaging
- 16.2.8.8 Immunohistochemistry (EpCam) Sample Collection
- 16.2.8.9 Extravesical Disease Evaluation
- 16.2.8.10 Post-Treatment Follow-Up
- 16.2.8.11 Anti-Vicinium Antibodies Collection

Figures

- 14.1.5.1 Swim-Lane Plot: Time on Treatment by Disease Cohort
- 14.1.5.2 Swim-Lane Plot: Time on Treatment
- 14.2.1.3 Line Plot: Percentage of Complete Response Over Time
- 14.2.2.3.1 Kaplan-Meier Plot: Duration of Response
- 14.2.2.3.2 Kaplan-Meier Plot: Duration of Response for Patients Who Achieved CR at Month 3
- 14.2.2.3.3 Kaplan-Meier Plot: Duration of Response for Patients Who Achieved CR at Month 6
- 14.2.2.3.4 Kaplan-Meier Plot: Duration of Response for Patients Who Achieved CR at Month 9
- 14.2.2.3.5 Kaplan-Meier Plot: Duration of Response for Patients Who Achieved CR at Month 12
- 14.2.2.3.6 Kaplan-Meier Plot: Duration of Response by Instillation Subgroup
- 14.2.2.4.1 Histogram of Maintaining CR for at Least 1 Year Post-Induction Phase for Subjects with CR at Months 3, 6, 9, and 12
- 14.2.2.4.2 Histogram of Maintaining CR for a Duration of at Least 1 Year for Subjects with CR at Months 3, 6, 9 and 12
- 14.2.2.5 Swim-Lane Plot: Duration of Response
- 14.2.3.2 Kaplan-Meier Plot: Event-free Survival
- 14.2.4.2.1 Kaplan-Meier Plot: Cystectomy-Free Days by Cohort
- 14.2.4.2.2 Kaplan-Meier Plot: Cystectomy-Free Days for Responders vs Non-Responders
- 14.2.5.2.1 Kaplan-Meier Plot: Time to Disease Recurrence – Cohort 3
- 14.2.5.2.2 Swim Lane Plot: Time to Disease Recurrence – Cohort 3
- 14.2.6.2 Kaplan-Meier Plot: Progression-free Survival
- 14.2.7.2 Kaplan-Meier Plot: Overall Survival
- 14.3.4.1.2 Spaghetti Plot: Clinical Laboratory Assessments by Visit – Subjects with a Treatment Emergent Grade 3 or Higher Event
- 14.3.4.1.3 Scatter Plot: Alanine Aminotransferase by Visit vs. Baseline
- 14.3.4.1.4 Scatter Plot: Alkaline Phosphatase by Visit vs. Baseline
- 14.3.4.1.5 Scatter Plot: Aspartate Aminotransferase by Visit vs. Baseline
- 14.3.4.1.6 Scatter Plot: Bilirubin by Visit vs. Baseline
- 14.3.4.1.7 Scatter Plot: Creatinine by Visit vs. Baseline
- 14.3.4.1.8 Scatter Plot: Hemoglobin by Visit vs. Baseline
- 14.3.4.1.9 Scatter Plot: Leukocytes by Visit vs. Baseline
- 14.3.4.1.10 Scatter Plot: Lymphocytes by Visit vs. Baseline
- 14.3.4.1.11 Scatter Plot: Neutrophils by Visit vs. Baseline
- 14.3.4.1.12 Scatter Plot: Platelets by Visit vs. Baseline

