3.4. TIMING OF ANALYSES

A Data Safety Monitoring Board (DSMB) will review aggregated safety and limited efficacy data on a biannual basis.

An analysis of safety and limited efficacy data will be conducted once all subjects have completed 3, 6, and 12 months of follow-up.

A final analysis of all data will be conducted once all subjects enter the off-treatment period and the resulting data have been cleaned and quality assured, and the database locked.

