5.2. EFFICACY ANALYSIS

5.2.1. Primary Efficacy Endpoint

The primary outcome measure is the complete response rate in subjects with refractory /relapsed CIS or CIS plus papillary disease (i.e., cohorts 1 and 2) following the initiation of Vicinium therapy.

Patients who discontinue or die before Month 3 will be included in the denominator of the primary analysis.

For the primary efficacy endpoint analysis, the following conventions will be utilized in determining treatment failure or complete response at a given visit.

1. Subjects that have centrally read pathology findings ('CIS', 'any-grade T1', 'high-grade Ta') or centrally read cytology results ('High Grade Urothelial Carcinoma') that indicate treatment failure for a given visit will be considered to have treatment failure.
2. Subjects who met a treatment failure criterion at a previous visit are treatment failures at all subsequent visits.
3. Subjects who have discontinued the study on or prior to the visit and have missing data that would be necessary to generate response are considered non-CRs.
4. Subjects who do not meet criterion 1-3 are complete responders.

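### Interim Table 13 drops ongoing subjects but, under the SAP's response rules, keeps early failures, so complete response runs low at visits not all subjects have reached

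*SAP*

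**What the plan says.** SAP 3.4 sets the occasions: "A Data Safety Monitoring Board (DSMB) will review aggregated safety and limited efficacy data on a biannual basis", with no minimum follow-up, and "An analysis of safety and limited efficacy data will be conducted once all subjects have completed 3, 6, and 12 months of follow-up". The output lists for the DSMB (SAP 10) and for the 6-month analysis (SAP 11) each contain one CR summary, under the same title: "Table 13 Summary of Complete Response by Visit, Ongoing Subjects Are Excluded as 'Missing', mITT Population". Neither list defines an ongoing subject, names the visits to be shown, or gives the denominator at each visit.

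Rules for calling a subject a responder or a failure at a visit appear only in SAP 5.2.1, introduced by "For the primary efficacy endpoint analysis, the following conventions will be utilized in determining treatment failure or complete response at a given visit". Rule 1 assigns failure from central pathology or cytology. Rule 2 reads "Subjects who met a treatment failure criterion at a previous visit are treatment failures at all subsequent visits". Rule 3 counts as non-responders "Subjects who have discontinued the study on or prior to the visit and have missing data that would be necessary to generate response". Rule 4 is the default: "Subjects who do not meet criterion 1-3 are complete responders". None of the four mentions a data cut-off.

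On percentages, SAP 9 refers to the total count of the categories shown: "Percentages should be calculated using this total as the denominator". Subjects excluded as missing therefore leave the denominator. Protocol 11.3 takes a subject with treatment failure off study drug, so a failed subject is not ongoing on treatment and the exclusion in the table title does not remove that subject.

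**The concern.** Take two subjects first dosed on the same day, four months before a data cut. One fails at Month 3. Under rule 2 that subject is a failure at Months 6, 9 and 12 as well, and stays in those columns. The other is in response at Month 3 and still on treatment, and is dropped from the same columns as missing. Follow-up is identical, so inclusion depends on outcome. The later columns then collect recent failures without the recent responders who belong beside them.

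The later columns are where a reader looks for durability. Table 13 is the only CR summary table listed for the DSMB, so an understated rate at Months 6 to 12 could colour its view of benefit and risk.

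**Working it through.** Months count from first dose: Month 3 is the post-induction evaluation, Month 6 is Week 26, and so on every 13 weeks.

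**The plan's own figures.** The documents state no interim CR rate, so there is none to reproduce. The one relevant number is the design assumption in SAP 3.1 of 30% CR at 12 months. The interval table beside it does reproduce (exact lower limit 0.2002 at N = 76, stated as 0.200), but it does not bear on Table 13.

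**Assumptions.** Uniform accrual, failures found at the 3-monthly visits, no drop-out. Neither the accrual length nor a response curve is given, so both are varied:
- Curve A: 40/28/21/17% at Months 3/6/9/12.
- Curve B: 40/36/33/30%, set to meet the SAP's 30% at Month 12.
- Curve C: 44/31/22/16%, with end points from the Phase 2 results in Protocol 7 (44% CR, 16% disease-free at one year).
- Accrual of 12, 24 or 30 months. The synopsis's 36-month study period less 24 months of treatment suggests about 12.

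**Formula.** Let p be the share of treated subjects who have reached visit v, S(v) the true CR rate there, and q(u) the share whose latest reached visit is an earlier visit u. Then

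Table 13 rate = p × S(v) / [p + Σ q(u) × (1 − S(u))].

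The sum is the early failures carried into a visit they have not reached. It is zero once everyone has reached v and positive otherwise, so the error can only be downward. Limiting the denominator to those who have reached v gives p × S(v) / p = S(v).

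**DSMB cut 12 months after the first subject, curve A, 24-month accrual.** Follow-up is uniform on 0 to 12 months, so each 3-month band holds 0.25 of those treated.
- Month 3: nobody has an earlier scheduled visit, so the rate is 40%, as it should be.
- Month 6: 0.50 × 0.28 / (0.50 + 0.25 × 0.60) = 0.140 / 0.650 = 21.5%, true 28%.
- Month 9: 0.25 × 0.21 / (0.25 + 0.25 × 0.72 + 0.25 × 0.60) = 0.0525 / 0.580 = 9.1%, true 21%.

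With curve B the same cut gives 27.7% against 36% at Month 6 and 14.7% against 33% at Month 9.

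**6-month analysis, curve A, 24-month accrual.** Follow-up is uniform on 6 to 30 months, so each band holds 0.125.
- Months 3 and 6: all subjects have reached them, so there is no error.
- Month 9: 0.875 × 0.21 / (0.875 + 0.125 × 0.72) = 0.18375 / 0.965 = 19.0%, true 21%.
- Month 12: 0.75 × 0.17 / (0.75 + 0.125 × 0.79 + 0.125 × 0.72) = 0.1275 / 0.93875 = 13.6%, true 17%.

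**6-month analysis, Month 12 column, by accrual length:**

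| Accrual | Curve B (true 30%) | Curve C (true 16%) |
|---|---|---|
| 12 months | 0.150 / 0.8275 = 18.1% | 9.2% |
| 24 months | 0.225 / 0.91375 = 24.6% | 12.9% |
| 30 months | 0.240 / 0.931 = 25.8% | 13.5% |

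**The case against.** The strongest objection is that the premise is inferred. SAP 5.2.1 is written for the primary endpoint analysis and does not name Table 13. Subsequent visits could mean only those a subject could have reached by the cut-off, and then there is no bias. This stands as a condition on the conclusion. The inference is still a strong one. No other per-visit CR rules exist, and the exclusion of ongoing subjects looks like a correction to rule 4, which would otherwise make them responders at visits they have not reached. No matching correction is written for failures. On either reading the denominator is unstated.

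A reader might infer that all interim CR rates are too low. The documents do not support that. Month 3, the SAP's primary response time point, is essentially unbiased; only failures at unscheduled evaluations or discontinuations before Month 3 could disturb it. The 6-month table is affected only if it prints visits after Month 6.

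It is also tempting to cite the Month 12 column at the 12-month cut, where the formula gives 0%. That does not measure a correctable error: nobody has reached the visit, SAP 9 suppresses the percentage for a zero count, and a correct denominator would give no rate either.

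The practical stakes are limited. Protocol 17.7 plans no formal interim analysis, and Protocol 15.1 describes DSMB review of aggregated safety data. The DSMB also receives the efficacy listing and time-on-treatment figures, and SAP 9 already asks for contributing sample sizes. A mismatch with the final CR table proves little, because that table uses a different population. All of this stands. It lowers the consequence without making the later columns correct, and a printed N does not reveal that it was selected by outcome.

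**Conclusion.** The concern holds conditionally. If Table 13 follows SAP 5.2.1, its CR rates are biased low at every visit not all subjects have reached by the cut-off. The direction follows from the rules. The size rests on assumed accrual and response curves: about 6.5 points at Month 6 and 12 points at Month 9 for a 12-month DSMB cut under curve A, and about 4 to 12 points at Month 12 of the 6-month analysis under the SAP's 30%.

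A reader might go further and infer that the trial's efficacy result is compromised. It is not. The final analysis follows once all subjects are off treatment, its CR tables carry no exclusion of ongoing subjects, and no stopping rule or alpha depends on Table 13. What should be corrected is a stated exclusion rule that can misreport durability in the DSMB's only CR summary table.

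**What to change.** In Table 13 of SAP 10 and SAP 11, and in the same table if it is produced for the 3- and 12-month analyses, replace the exclusion of ongoing subjects with a denominator rule. At each visit, include every subject whose time since first dose at the cut-off reaches the scheduled assessment plus its permitted window, whatever the outcome. Apply rules 1 to 4 of SAP 5.2.1 within that set, print its N, and show no rate where nobody is eligible. Report how many eligible subjects still have results pending, because rule 4 would otherwise count them as responders. A Kaplan-Meier estimate using all subjects is an optional addition. Interim tables already issued under the present title need a footnote or a rerun if failures were carried to unreached visits.

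The cost is a sentence in each output list, minor reprogramming, and smaller numbers in the late columns of early tables.
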